5.7.2 Prohibited Concomitant Vaccines and Concomitant Therapy

Receipt of non-study COVID-19 vaccine is prohibited for all enrolled participants while on study. Participants in Cohort B must have received both doses of BNT162b2 vaccine at least 5 months prior to study enrollment.

The use of the following concomitant medications and/or vaccines will not require withdrawal of the participant from the study but may determine a participant's eligibility to receive a second dose or evaluability in the per-protocol analysis:

- Any investigational or non-registered product (drug or vaccine) other than the study vaccine used during the study period.
- A non-study, live, attenuated vaccine administered during the period from 28 days before through 28 days after each dose of study vaccine or any approved inactivated or recombinant vaccine that was administered within 14 days before or after any dose of study vaccine.
- Immunoglobulins and/or any blood products administered during the study period (except for treatment of COVID-19).
- Medications that suppress the immune system, including corticosteroids administered at doses of 20 mg prednisone equivalent/day or higher, with the exception of medications used in the treatment of COVID-19.

Section 4.2.1 describes delay in vaccination that will occur in the event of analgesic/antipyretic use prior to planned study vaccination.

If a participant receives/takes a prohibited vaccine or drug therapy, the Investigator and the CRO's Medical Monitor will make a joint decision about continuing or withholding further dosing from the participant based on the time the medication was administered, the drug's pharmacology and pharmacokinetics, and whether use of the medication will compromise the participant's safety or the interpretation of data. It is the Investigator's responsibility to ensure that details regarding concomitant medications and vaccines are adequately recorded in the eCRF. All medication and interventions necessary for the appropriate care for the study participant, particularly to treat COVID-19, should be administered and appropriately documented along with the AE.

5.7.3 Concomitant Procedures

A concomitant procedure is any therapeutic intervention (e.g., surgery/biopsy, physical therapy) or diagnostic assessment (e.g., blood gas measurement, bacterial cultures) performed between signing of the informed consent and the participant's last protocol-specified study visit.

All concomitant procedures must be recorded in the eCRF until 28 days after receipt of the last study vaccine. Thereafter, only concomitant procedures associated with an SAE, MAAE, AE leading to discontinuation of study vaccine/study withdrawal or treatment/evaluation of COVID-19 cases will be entered in the eCRF.

5.7.4 Rescue Medication

Epinephrine for SC injection, diphenhydramine for intravenous injection, and any other medications and resuscitation equipment for the emergency management of anaphylactic reactions must be available in close proximity in the room where the vaccination is administered.

5.8 Dose Modification

No dose modifications will be allowed.

5.9 Intervention After the End of the Study

No intervention will be provided to study participants at or after the EOS.

6 STUDY ASSESSMENTS AND PROCEDURES

6.1 Study Procedures

6.1.1 Physical Examinations

A complete physical examination will include, at a minimum, assessments of the general status of the participant, the skin of the intended study vaccine administration site, superficial lymph nodes, and cardiovascular, respiratory, gastrointestinal, and neurological systems.

A directed physical examination will include, at a minimum, assessments of the skin of the intended/actual study vaccine administration site and/or any organ systems relevant to symptoms or AEs reported by the participant. Investigators should pay special attention to clinical signs related to previous serious illnesses.

Physical examination is to be performed by a qualified health care practitioner designated by the Investigator.

Any clinically significant change found during a physical examination should be evaluated for an underlying cause and the associated AE reported (Section [6.3.1](#)). If no known cause is determined, the clinically significantly abnormal parameter may be reported as an AE.

6.1.2 Vital Signs and Body Temperature

VS comprise heart rate (HR), blood pressure and respiratory rate.

VS will be measured in a semi-supine position after 5 minutes of rest. VS and body temperature will be evaluated for clinical significance. Any clinically significant change in VS and body temperature should be evaluated for underlying cause and the associated AE reported. If no known cause is determined, the clinically significantly abnormal parameter may be reported as an AE.

After each study vaccine administration, vital signs should be checked, and repeat vital signs should be taken if clinically indicated.

6.1.3 Pregnancy Testing

Pregnancy testing will be performed on women who are not surgically sterile or confirmed postmenopausal. Pregnancy testing by urine dipstick is acceptable. Pregnancy testing will be performed and evaluated prior to each study vaccine administration. Refer to the Schedule of Assessments ([Appendix 1](#) and [Appendix 2](#) for Cohorts A and B, respectively) for further details.

6.1.4 Safety Blood Sampling

Procedures for collection, handling, and storage of blood collected for safety assessments will be detailed in the Laboratory Manual. A list of laboratory analytes to be tested is included in [Appendix 3](#).

6.1.5 Nasopharyngeal Swab Sampling

Procedures for collection, handling, and storage of swabs collected for confirmation of SARS-CoV-2 infection will be detailed in the Laboratory Manual.

6.1.6 Immunogenicity Blood Sampling

Procedures for collection, handling, storage, and shipment of blood samples collected to assess the participant's immune response will be detailed in the Laboratory Manual.

6.1.7 Diary Card Procedures

Paper Diary Cards will be distributed to participants at each study vaccination visit. They will be instructed to complete the Diary Card for 7 days post-vaccination. Compliance will be checked at the study visits that are conducted 3 and 7 days after each study vaccination. Diary Cards are source documents and should be collected on Day 8 (Cohort A and Cohort B) and Day 36 (Cohort A) visits and maintained in the participants' study files. Data from the diary card must be transcribed verbatim into the electronic data capture system.

6.2 Study Assessments and Visits

6.2.1 Cohort A Visits

The Schedule of Assessments for Cohort A (including Sub-cohorts A1 and A2) is located in [Appendix 1](#).

Participants in Cohort A are followed for 12 months post-second dose of the study vaccine until Day 394. Study vaccines are administered on Days 1 and 29 where safety and immunogenicity assessments are also performed prior to administration of the study vaccine. Clinic visits including safety laboratories should occur 3, 7, and 28 days post-vaccination (Days 4, 8, 29, 32, 36, and 57). Clinic visits including blood collection to measure the participant's immune response to the study vaccine should occur on Days 15, 29, 43, 57, 119, 209, 299, and 394 (Final Visit).

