Primary Objectives and Primary Endpoints	
Objective 1: To describe the safety and reactogenicity of 3 investigational SARS-CoV-2 self-amplifying RNA vaccines
 
Endpoint 1: Safety will be summarized for each vaccination as the number and percentage of participants with the following:
 
 a. Any solicited local or systemic adverse event (AE) collected for 7 days after each study vaccination, which will be assessed by toxicity grade b. Any unsolicited AE collected for 28 days after each study vaccination, which will be assessed by severity and relationship to study vaccine c. Any medically attended adverse events (MAAEs), AEs leading to discontinuation from study vaccine/study withdrawal, or serious

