6.3.1.2.8 Eliciting and Documenting Adverse Events

AEs will be assessed from the time the participant signs the informed consent form (ICF) until exit from the study. Safety follow-up will be continued for 12 months after last injection of the study vaccine (up to last study visit). Any ongoing AE that a participant is experiencing at the time of Screening (e.g., intercurrent illness) should be captured as medical history.

Solicited AEs will be solicited by Paper Diary for 7 days after each study vaccination in all participants.

At every clinic visit and daily (for 7 days after each vaccination) by Paper Diary, participants will also be asked a standard nonleading question to elicit any medically related changes in their well-being. Any and all new changes to the participant's health (including exacerbation of underlying disease) that are not solicited events will be regarded as an unsolicited AE.

In addition to participant observations, AEs identified from any study data (e.g., clinically significant findings or changes on physical examination, safety laboratory assessments, VS) or identified from review of other documents (e.g., participant Paper Diary) that are relevant to participant safety will be documented on the AE page on the eCRF.

All unsolicited AEs will be collected for 28 days after each study vaccination. Unsolicited AEs that meet the protocol definition of MAAE, SAE, or AEs leading to discontinuation of the study vaccine/study withdrawal will be captured for the duration of study participation.

If the Investigator learns of any SAE, including a death, at any time after a participant has been discharged from the study, and he/she considers the event to be reasonably related to the study vaccine or study participation, the Investigator must promptly notify the Sponsor.

Solicited and unsolicited AEs will be coded by System Organ Class (SOC) and Preferred Term (PT) according to the Medical Dictionary for Regulatory Activities (MedDRATM). Note: Injection site tenderness will be coded only to the lower-level term, as there is no PT of injection site tenderness (it codes to a PT of injection site pain).

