13 APPENDICES

APPENDIX 1 SCHEDULE OF ASSESSMENTS - COHORT A (INCLUDING A1 AND A2)

Visit Type:	Screening	Vaccination Visit	Post Vax Day 4/32 Visit	Post Vax Day 8/36 Visit	Post Vax Day 15/43 Visit	Post Vax Day 57 Visit	Post Vax Day 119/209/299 Visit	Unscheduled Visit	ET Visit	Final Visit
	Clinic ^a	Clinic ^a	Clinic ^a	Clinic ^a	Clinic ^a	Clinic ^a	Clinic ^a	Clinic ^{a, b}	Clinic ^a	Clinic ^a
Study Day:	-28 to -1	1, 29	4, 32	8, 36	15, 43	57	119, 209, 299	N/A	N/A	394^c
Visit Window (days):	0	+1 (Day 29 Only)	+1	+1	+1	±3	±7	N/A	N/A	+14
Informed consent	X									
Weight/height	X									
Review of inclusion/exclusion criteria	X									
Pregnancy test ^c	X	X								
Screening visit blood sampling ^d	X									
Physical examination ^c	X	X	X	X	X	X	X	X	X	X
Vital signs and body temperature ^f	X	X	X	X	X	X	X	X	X	X
Medical history	X									
Review for COVID-19 symptoms and exposure ^g	X	X	X	X	X	X	X	X	X	X
Blood for safety testing ^h	X	X	X	X		X				

Visit Type:	Screening	Vaccination Visit	Post Vax Day 4/32 Visit	Post Vax Day 8/36 Visit	Post Vax Day 15/43 Visit	Post Vax Day 57 Visit	Post Vax Day 119/209/299 Visit	Unscheduled Visit	ET Visit	Final Visit
	Clinic ^a	Clinic ^a	Clinic ^a	Clinic ^a	Clinic ^a	Clinic ^a	Clinic ^a	Clinic ^{a, b}	Clinic ^a	Clinic ^a
Study Day:	-28 to -1	1, 29	4, 32	8, 36	15, 43	57	119, 209, 299	N/A	N/A	394 ^c
Visit Window (days):	0	+1 (Day 29 Only)	+1	+1	+1	±3	±7	N/A	N/A	+14
Study vaccine administration ⁱ		X								
Post-vaccination observation ^j		X								
Blood sampling for immunogenicity antibody testing ^k		X			X	X	X		X	X
Blood sampling for T-cell responses ^l		X			X	X	X (Day 209 only)		X	X
Archival of serum sample ^m		X			X	X	X		X	X
Archival of PBMC sample ⁿ		X			X	X	X (Day 209 only)		X	X
Sample for SARS-CoV-2 ^o								X		
Pulse oximetry								X		
Adverse events ^p	X	X	X	X	X	X	X	X	X	X

Visit Type:	Screening	Vaccination Visit	Post Vax Day 4/32 Visit	Post Vax Day 8/36 Visit	Post Vax Day 15/43 Visit	Post Vax Day 57 Visit	Post Vax Day 119/209/299 Visit	Unscheduled Visit	ET Visit	Final Visit
	Clinic ^a	Clinic ^a	Clinic ^a	Clinic ^a	Clinic ^a	Clinic ^a	Clinic ^a	Clinic ^{a, b}	Clinic ^a	Clinic ^a
Study Day:	-28 to -1	1, 29	4, 32	8, 36	15, 43	57	119, 209, 299	N/A	N/A	394 ^c
Visit Window (days):	0	+1 (Day 29 Only)	+1	+1	+1	±3	±7	N/A	N/A	+14
Concomitant medication, vaccinations, and procedure collection ^q	X	X	X	X	X	X	X	X	X	X
Diary compliance check ^r			X	X						
Counseling about long-term follow-up for SARS-CoV-2 infection ^s									X	

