- i The study vaccine will be administered by intramuscular injection into the lateral aspect of the deltoid muscle of the nondominant arm, where possible. The study vaccine will be administered in an observer-blind fashion.
- j Vaccinated participants will be observed at the site for at least 30 minutes following study vaccine administration and until clinically stable. After each study vaccine administration, vital signs should be checked, and repeat vital signs should be taken if clinically indicated.
- k Blood samples will be taken for antibody immunity testing at each time point noted; additional tube(s) of blood will be drawn at Day 29 and Day 57 for potential use in non-clinical passive transfer studies.
- l Blood samples will be taken for assessment of cell-mediated immunity testing at each time point noted.
- m Stored at -70°C for follow-up immunological assessments or exploration of laboratory findings and/or adverse events.
- n Stored at -70°C for follow-up immunological assessments or exploration of laboratory findings.
- o Use of provided SARS-CoV-2 test kit to be sent to a designated laboratory is strongly preferred. Approved alternate measures of virological confirmation of SARS-CoV-2 may be performed if it is not feasible to use provided kits.
- p Solicited AEs will be collected by paper Diary Cards for 7 days after each study vaccination for all participants. All unsolicited AEs will be collected through Screening and 28 days after each vaccination and if associated with an unscheduled visit. SAEs, MAAEs, and AEs leading to discontinuation of the study vaccine/study withdrawal are to be collected through the end of study participation.
- q Concomitant medications and procedures are to be collected from Screening through Day 28 following last vaccination and if associated with an unscheduled visit. Concomitant medications and procedures associated with SARS-CoV-2 infection/COVID-19 disease, SAEs, MAAEs and AEs leading to discontinuation of the study vaccine/study withdrawal are to be collected through to the end of study participation. Concomitant vaccinations are to be collected as early as 28 days prior to receipt of the first dose of study vaccine and through the end of study participation.
- r A compliance check is performed by site staff review of the paper Diary Card to confirm that the participant is entering the requested responses.

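### The Cohort A Day 57 visit may be held up to 3 days early, so the last scheduled AE interview after dose 2 can precede the end of the 28-day collection period of primary endpoint 1b

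*Protocol*

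**What the plan says.** The Synopsis defines primary endpoint 1, item b, as "Any unsolicited AE collected for 28 days after each study vaccination, which will be assessed by severity and relationship to study vaccine". Table 2 repeats it. Protocol Section 6.3.1.2.8 sets the matching collection rule: "All unsolicited AEs will be collected for 28 days after each study vaccination". After that, only SAEs, MAAEs and AEs leading to discontinuation or withdrawal are captured for the rest of participation. Footnote p of Appendix 1 words the rule slightly differently: "All unsolicited AEs will be collected through Screening and 28 days after each vaccination and if associated with an unscheduled visit".

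Section 6.2.1 states "Study vaccines are administered on Days 1 and 29" and then fixes the safety visits: "Clinic visits including safety laboratories should occur 3, 7, and 28 days post-vaccination (Days 4, 8, 29, 32, 36, and 57". Day 57 is thus the visit that closes the period after dose 2.

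In Appendix 1 the study days run "1, 29 4, 32 8, 36 15, 43 57 119, 209, 299", and the Visit Window row, whose first entry is +1, runs "1 (Day 29 Only) +1 +1 +1 ±3 ±7". The column headed "Post Vax Day 57 Visit" carries the ±3. Every Cohort A post-vaccination visit up to Day 43 carries +1 only. The next visit after Day 57 is Day 119 ±7, and no telephone contact is scheduled between them.

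The SAP (Section 4.6.2) tabulates unsolicited AEs within 28 days of each vaccination by term, severity and relationship. Protocol Section 7.5.3 summarises laboratory values at 3, 7 and 28 days after each dose.

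**The concern.** A visit that closes a fixed collection period should not fall before the period ends, unless something else covers the remaining days. Here it may, and the case does not depend on late dosing: it arises with dose 2 exactly on Day 29.

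Day 57 is the exception among the visits that close a 28-day period. The Cohort A Day 29 visit (closing dose 1) and the Cohort B Day 29 visit (closing the only dose) are both +1 and cannot be early. The documents give no reason for the difference.

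Three items are exposed:

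- **Unsolicited AEs after dose 2**, part of a primary endpoint reported for each vaccination. Any shortfall would be confined to dose 2 and would run in one direction relative to dose 1.
- **Concomitant medications**, which footnote q collects through 28 days after the last vaccination.
- **The 28-day safety laboratory sample.** SAP Section 4.1.2 summarises by nominal visit label, so a sample drawn at day 25 would be reported under Day 57 with nothing in the by-visit table to show it.

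**Working it through.** **Inputs.** Doses on Days 1 and 29, with +1 allowed for Day 29 (Section 6.2.1, Appendix 1). Closing visit Day 57 ±3 and next visit Day 119 ±7 (Appendix 1). Collection period 28 days (Synopsis, Section 6.3.1.2.8). Study day is counted from the first dose (SAP Section 4.1.4).

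**1. Reproduce the plan's visit days.** Dose 1: 1+3 = 4, 1+7 = 8, 1+28 = 29. Dose 2: 29+3 = 32, 29+7 = 36, 29+28 = 57. These match Section 6.2.1.

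**2. Apply the visit window.** Permitted days run from 57−3 = 54 to 57+3 = 60. The earliest visit is 54−29 = 25 days after an on-time dose 2, or 54−30 = 24 days after a Day 30 dose.

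**3. Find the end of the collection period.** The documents support two counts. Section 6.2.1 calls Day 57 28 days after vaccination, so dose day is day 0. The SAP's duration rule (Section 4.1.4) adds one day, so dose day is day 1.

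| Dose 2 | Dose day counted as | Period ends | Uncovered after a Day 54 visit | Share of 28 days |
|---|---|---|---|---|
| Day 29 | day 0 | 29+28 = Day 57 | 57−54 = 3 days | 10.7% |
| Day 29 | day 1 | 29+27 = Day 56 | 56−54 = 2 days | 7.1% |
| Day 30 | day 0 | 30+28 = Day 58 | 58−54 = 4 days | 14.3% |
| Day 30 | day 1 | 30+27 = Day 57 | 57−54 = 3 days | 10.7% |

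These are worst cases. With dose 2 on Day 29, visits on Days 54 to 56 (day-0 count) or Days 54 to 55 (day-1 count) precede the end of the period.

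**4. Time to the next scheduled contact.** Day 119 ±7 is Day 112 to Day 126. From a Day 54 visit that is 112−54 = 58 to 126−54 = 72 days. An AE starting on Days 55 to 57 would next be asked about 112−57 = 55 to 126−55 = 71 days after onset, or about 8 to 10 weeks.

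**5. Compare the other closing visits.** Cohort A Day 29 +1 falls 29−1 = 28 to 30−1 = 29 days after dose 1. Cohort B Day 29 +1 also falls 28 to 29 days after its dose. Neither can be short on the day-0 count, nor therefore on the day-1 count.

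**6. Test the obvious repair.** Dropping only the minus days gives Days 57 to 60. After a Day 29 dose that is 28 to 31 days. After a Day 30 dose it is 27 to 30 days, still one day short on the day-0 count. A window tied to a fixed study day therefore does not fully close the gap; one tied to the dose 2 date does.

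**The case against.** The strongest reply is that the 28-day limit governs when an event starts, not when the participant is asked. On that reading an AE starting on Day 56 is in scope whenever it is reported, and the plan offers later chances to report it. Section 6.2.1.6 includes an AE interview at Day 119. Section 6.3.1.2.8 requires an open question at every clinic visit. Section 6.3.1.2.11 records non-serious AEs up to the last protocol visit. Section 6.7 asks participants to contact the site within 24 hours for a long list of common symptoms, with an unscheduled visit within 48 hours. Its exception for vaccine reactions covers only the first 7 days, and an AE leading to such a visit is an MAAE, collected to study end.

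This reply largely stands. A reader might infer that late-period AEs are lost because no scheduled interview can capture them; these sections contradict that. What survives is the quality of ascertainment. For an event that prompts no visit, the remaining routes are spontaneous report or long recall, at a visit by which footnote p has narrowed routine collection to the more serious categories.

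A reader might also infer that dose 2 rates are biased low, including against Cohort B. The documents do not establish that. The cohorts are analysed independently, no formal comparison is planned, and the visit window is the same for every vaccine under observer blinding, so no arm is favoured.

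Nor can an average loss be stated. Spreading visits evenly over Days 54 to 60 gives (3+2+1)/7 = 0.86 day, or (2+1)/7 = 0.43 day on the other count. But the documents give no distribution of visit dates, and the sum treats uncovered days as yielding no reports at all.

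**Conclusion.** The schedule and the endpoint do not fit together. A compliant closing visit can leave 2 to 3 days of the post-dose-2 period without a timely scheduled interview when dosing is on time, and 3 to 4 days when dose 2 is on Day 30. The Day 30 figures assume that Appendix 1's study days are read literally from the first dose; a site that counted from the actual second dose would have the on-time gap.

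The consequence is delayed, recall-dependent ascertainment, mainly of mild events that are not medically attended. Post-dose-2 rates may be slightly under-ascertained relative to dose 1, to an extent that cannot be computed from the documents. Exposure is limited to the planned 36 Cohort A participants, and within them to those seen early. The same window allows the nominal 28-day laboratory sample at day 25 after an on-time dose. In a small descriptive study this is a minor point, worth correcting because the correction is so cheap.

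**What to change.** In Appendix 1, define the visit by the actual dose 2 date: dose 2 plus 28 days, 0 to +3, with no early allowance. This also brings the safety laboratory sample to at least 28 days.

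If ±3 is kept for scheduling reasons, add a footnote requiring a brief telephone contact on AEs and concomitant medications once 28 days have passed since dose 2, for anyone seen early. This repairs AE and medication collection but not the timing of the laboratory sample.

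Either change is one table entry or footnote at the next amendment. The cost is three fewer days of scheduling flexibility, or a short call.

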6.2.1.1 Screening

At Screening, individuals willing to participate in the study will:

1. Review and provide informed consent
2. Have an interview to review the following:
 - a. Medical history
 - b. Current symptoms
 - c. Risks of recent exposure to COVID-19 and for symptoms of COVID-19
 - d. AEs
 - e. Concomitant medications, vaccinations, and procedures
 - f. Availability for study procedures
3. Have a complete physical examination
4. Take a pregnancy test (if the participant is a woman of childbearing potential). Blood sampling may be performed for the pregnancy test if urine testing is not permitted by site policy. A follicle-stimulating hormone (FSH) test will be given to women suspected to be menopausal. Refer to [Appendix 4](#).
5. Undertake a blood draw for Screening laboratories (refer to [Appendix 1](#) and [Appendix 3](#) for a list of Screening assessments)

6. Have their VS measurements taken (HR, respiratory rate, blood pressure, and body temperature)
7. Have their height and weight measurements taken

The information gathered from the interview and the assessments will be evaluated against inclusion/exclusion criteria to determine study eligibility.

